5 STUDY DESIGN

5.1 Overall Design

This is a pragmatic, single center randomized quality improvement trial to evaluate a clinician-facing implementation strategy to increase the use of evidence-based practices (EBPs) to reduce bleeding in patients who are using anticoagulant-antiplatelet therapy (AAT) and who are managed by the Michigan Medicine anticoagulation monitoring service. A clinician-level strategy will be evaluated and compared to usual care: clinician notification with nurse facilitation (CNNF) consists of an EHR message that identifies the patient as high-risk for upper GI bleeding and

suggests either discontinuing the antiplatelet agent or initiating a PPI and in which a nurse undertakes multiple steps to overcome barriers to medication optimization. Clinicians will be cluster randomized, such that up to 4 patients cared for by each clinician will receive the same clinician-level notification.

5.2 Scientific Rationale for Study Design

The current study is a quality improvement trial that will evaluate the effectiveness of a novel quality improvement strategy to reduce the risk of upper GI bleeding in patients using AAT.

Clinician notification is commonly used by the anticoagulation service as part of routine clinic practice to improve the safety of patients using warfarin. For example, the anticoagulation clinic previously undertook a quality improvement project that consisted of notifications to clinicians about the potential benefits of discontinuing aspirin in certain patients. However, even though these clinician-facing strategies are considered standard practices, it remains important for the clinic to understand the extent to which such strategies are effective, and whether they justify the significant resource investment of the anticoagulation clinic staff. This study will help to answer that question in the context of medication optimization to reduce upper GI bleeding.

The anticoagulation clinic eventually plans to use CNNF with all eligible patients. However, because deployment of CNNF requires additional effort by the nursing staff, only a limited number of patients (n=28) can be delivered CNNF each week. Therefore, we will use a “wait-listed design,” in which each week patients will be randomized to either have their clinicians receive CNNF or be included in wait-list control group. The patients in the wait list control group will serve as comparators to the patients who received CNNF, allowing for valid causal inference about the effect of CNNF compared to usual care. This design is often used to evaluate the effectiveness of interventions that are planned for a wider rollout because they are considered fair by patients in the setting of limited capacity to rollout the intervention all at once. At the completion of the study, the patients who were randomized to the wait-list control group will receive the quality improvement strategy.

5.3 Justification for Intervention

Upper GI bleeding is a serious risk to patients who use AAT. However, both medication optimization EBPs to reduce upper GI bleeding risk are underused.

This trial will rigorously evaluate a clinician outreach approach that is commonly used by the anticoagulation service to improve the safe use of warfarin.

5.4 End-of-Study Definition

Patients are considered to have completed the study after week 25.

Clinicians are considered to have completed the study 10 weeks after trial entry of the last patient within the clinicians' cluster.

6 STUDY POPULATION

6.1 Sample size

The target sample size for the study is 220 patients cared for by 110 target clinicians. See sample size determination (below) for a justification of the size.

6.2 Inclusion Criteria

For patients:

- Enrollment with the Michigan Medicine anticoagulation monitoring service
- Currently prescribed warfarin with anticipated use for ≥ 90 days on day 1 of trial enrollment, according to the MiChart documentation.
- Currently prescribed an antiplatelet drug (aspirin, clopidogrel, ticagrelor, or prasugrel) according to the MiChart medication list

For clinicians:

- Cardiologists at Michigan Medicine who in the prior year had a face-to-face or virtual visit with a patient who meets eligibility criteria
- Michigan Medicine primary care providers for patients who meet eligibility criteria
- Clinicians in any specialty who are designated as the clinician of record with the anticoagulation clinic for a patient who meets eligibility criteria

6.3 Exclusion Criteria

For patients:

- Age less than 18
- Currently prescribed a PPI
- Documented intolerance or allergy to PPI use
- Left ventricular assist device
- Heart transplant
- Participation in a previous pilot study of these QI strategies

For clinicians:

- Cardiologists specializing in electrophysiology or saw the patient for a clinic visit related to a TAVI procedure unless they are the clinician of record for a patient followed by the anticoagulation service who does not have a Michigan Medicine PCP.
- Participation in a previous pilot study of these QI strategies

6.4 Patient and Clinician Selection

Since this evaluation is part of a quality improvement initiative, we will include 220 patients who may benefit from medication optimization. These patients will be identified using a report developed in the EHR. The same report will identify the “target clinician” for each eligible patient. A patient’s target clinician is defined as, in order of descending priority, either a (non-electrophysiologist) Michigan Medicine cardiologist (excluding TAVI visits) who has seen the patient in the prior year (if one exists), or else a Michigan Medicine PCP for the patient, or else the patient’s clinician of record for the anticoagulation monitoring service.

All target clinicians will be randomized to receive CNNF or usual care. Eligibility will be determined based on information in the electronic health record. All participants will be screened for eligibility in the week prior to study entry.

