1.2 Schema

1.3 Schedule of Activities

It is anticipated that 110 clinicians will be included in the study, and 220 patients who are cared for by those clinicians. QI strategies will be delivered to clinicians of eligible patients by

anticoagulation clinic nursing staff. Up to 50-56 patients will enter the study each week for 5 weeks (or longer if fewer patients enter each week).

For informational purposes, whether the evaluation vs. the anticoagulation clinic staff performs the activity is indicated in bold. Failure of the anticoagulation clinic staff to follow the clinical protocols for delivery of the clinician- level QI strategies will not be considered study deviations.

Schedule of Activities

Activity	Screening and randomization	Week 1	Week 2-5	Week 7-10	Week 11-25
Eligibility determination of clinicians and patients (research team)	X				
Cluster randomization of patients to CNNF vs. usual care (research team)	X				
Clinician delivery of CNNF for patients randomized to receive it (anticoagulation clinic staff)		X	X		
Additional outreach, communication, or facilitation steps for patients and clinicians as per anticoagulation clinic protocol for CNNF recipients (anticoagulation clinic staff)		X	X		
Patient phone survey, with waiver of informed consent (research team)				X	
Chart review to ascertain exploratory outcomes (research team)	X	X		X	X

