6.5 Screen Failures

Patients who are ineligible for the study at the time of screening will not be included.

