9 STUDY ASSESSMENTS AND PROCEDURES

9.1 Eligibility Assessment

All eligible patients will be identified using a MiChart workbench report prior to the start of the study. Eligibility will be assessed based on information in the EHR. Each week, it is anticipated that 42 patients will be randomized to receive either CNNF or usual care, and that 21 will have CNNF directed at their target clinicians. Each anticoagulation nurses will deliver CNNF to up to 4 patients each week but may deliver CNNF to fewer some weeks depending on staffing. At the start of each week, eligibility will be re-assessed for patients anticipated to receive the QI strategy in the coming week.

Similarly, clinician eligibility will be determined at the start of the trial and at the beginning of each week to ensure that only actively practicing Michigan Medicine clinicians are included.

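### Eligibility is re-checked after a clinician's arm can already be fixed, using criteria that overlap with the endpoint, so inclusion can depend on arm

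*Combined protocol and SAP*

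**What the plan says.** Sections 5.1 and 7.3 randomise clinicians, with up to 4 patients each, so all of a clinician's patients share one arm. Section 1.3 gives the pace of entry: "Up to 50-56 patients will enter the study each week for 5 weeks", or longer if fewer enter each week. Section 5.4 has a clinician finish "10 weeks after trial entry of the last patient within the" cluster, which implies that one clinician's patients can enter at different times.

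On screening, section 6.4 says: "All participants will be screened for eligibility in the week prior to study entry". Section 6.5 adds: "Patients who are ineligible for the study at the time of screening will not be included". Section 9.1 says: "At the start of each week, eligibility will be re-assessed for patients anticipated to receive the QI strategy in the coming week".

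On eligibility, section 6.3 excludes a patient who is "Currently prescribed a PPI", and section 6.2 requires "Currently prescribed an antiplatelet drug (aspirin, clopidogrel, ticagrelor, or prasugrel) according to the MiChart medication list".

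The primary endpoint (section 4) is self-reported stopping of all antiplatelet drugs, or starting and adhering to a PPI, at week 7-10. Section 11.2 specifies an ITT approach for the primary and secondary endpoints without defining the analysis set.

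**The concern.** The eligibility criteria mirror the endpoint. Once either kind of success is recorded in the electronic record, a patient who has not yet entered no longer qualifies. If this is checked after the clinician's arm is known, inclusion can depend on arm in two ways.

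- **Carry-over.** A CNNF clinician who is messaged about one patient may also change drugs for another who is due to enter later. That patient then fails the pre-entry screen. The intervention does not trigger this in usual care.
- **Unequal checking.** Read literally, section 9.1 re-checks only patients about to receive CNNF. A drug change for any reason before entry could then remove a CNNF patient, while a similar usual-care patient stays in and may count as a success. This needs no carry-over.

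Either route removes successes from the CNNF arm only. The result would be an underestimate of the effect that the clinic wants in order to judge whether the nursing effort is justified (section 5.2).

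**Working it through.** **1. The plan's own figure.** Inputs from section 11.1: 5% vs 35%, two-sided 5%, 90% power, ICC 0.95, mean 2 patients per clinician, CV 0.62, 20% dropout or ineligibility.

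- Unclustered n per arm, unpooled variance: (1.960 + 1.282)² × (0.05×0.95 + 0.35×0.65) / 0.30² = 32.1.
- Design effect: 1 + [(1 + 0.62²)×2 − 1]×0.95 = 2.680.
- 32.1 × 2.680 = 86.1 per arm, so 44 clinicians per arm and 176 patients. 176/0.8 = 220.

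The plan's numbers reproduce exactly, and this point does not touch them.

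**2. Share of CNNF patients who enter after a cluster-mate (L).** Assume that each patient's entry week is random over 5 weeks. For a cluster of m patients, L = 1 − Σ(w=1..5) (1/5)×[(6−w)/5]^(m−1).

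- m = 1, 2, 3, 4 gives L = 0, 0.40, 0.56, 0.64.
- An assumed size mix of 55/12/12/22% for 1 to 4 patients matches a mean of 2 and CV 0.62 (the shares are rounded). Per 100 clinicians it gives 55 + 24 + 36 + 88 = 203 patients. Of these, 0 + 9.6 + 20.2 + 56.3 = 86.1 enter later, so L = 0.42. I use 0.40.
- With a mean of 2, at least half of the patients are in their cluster's first entry week, so L cannot exceed 0.50.

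**3. Effect if screened-out patients are dropped.** Let s be the share of would-be successes among later entrants who are already changed in the record at the check. This is an assumption.

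- Fraction lost = 0.35 × L × s.
- Observed CNNF rate = (0.35 − lost)/(1 − lost).
- Power: effective n is 88/2.680 in usual care and 88×(1 − lost)/2.680 in CNNF, with unpooled variance. The loss is thus taken on top of the 20% allowance.

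Example, L = 0.40 and s = 0.25: lost = 0.035, which is 3.85 of 110 patients. The rate is 0.315/0.965 = 32.6%.

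| L | s | Lost of 110 | CNNF rate | Power |
|---|---|---|---|---|
| any | 0 | 0 | 35.0% | 90.6% |
| 0.25 | 0.25 | 2.4 | 33.5% | 87.6% |
| 0.40 | 0.10 | 1.5 | 34.1% | 88.8% |
| 0.40 | 0.25 | 3.85 | 32.6% | 85.5% |
| 0.40 | 0.50 | 7.7 | 30.1% | 78.5% |
| 0.50 | 0.50 | 9.6 | 28.8% | 74.2% |
| 0.50 | 1.00 | 19.2 | 21.2% | 45.9% |

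The last row is the extreme case, not an expectation.

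I have not sized the unequal-checking route. The nearest figure is the assumed 5% usual-care rate, which describes the outcome at follow-up and not the interval before entry.

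**4. When does randomisation happen?** The passages allow two readings.

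- *Randomised ahead of the check.* Section 9.1 identifies all eligible patients before the study starts, and section 8.1 refers to a gap between randomisation and delivery. If everyone randomised stays in ITT, the loss is zero.
- *Weekly cohorts.* Section 5.2 randomises each week, and section 9.1 anticipates 42 patients a week. Each cohort is then screened just before entry. Even so, a later patient of a clinician who has already been randomised is screened when that clinician's arm is fixed, and section 6.5 leaves out anyone who fails.

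No section chooses between these readings.

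**The case against.** The strongest reply is that the plan attaches no exclusion to the weekly re-check. Section 8.1 lists the reasons for withholding the strategy after randomisation: warfarin stopped, closed to the service, or target clinician changed. A new PPI or a stopped antiplatelet is not among them, and the stated consequence is non-delivery, not removal from analysis. With ITT in section 11.2, nothing need be lost. This stands as one possible reading. It does not settle the matter, because section 6.5 points the other way for anyone screened before entry, and section 8.1 does not say how undelivered patients are analysed.

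A second reply is that carry-over is unsupported. Each message concerns one named patient, the documents give no rate for action on patients not yet messaged, and the change must reach the record before the next check, which may be only days away. This also stands, so the figures are a range and not an estimate. Carry-over is still plausible, because the message also summarises guidance (section 7.1) that applies to the clinician's other patients on these drugs. Single-patient clusters and the first patients to enter in each cluster are unaffected by it.

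A reader might infer that the expectation of balance in section 11.5 is undermined too. The documents do not support that for the ITT analysis. That passage concerns patients already included who report at the call that they did not fit the criteria at the start. Patients screened out beforehand are not among them.

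**Conclusion.** The gap is real but conditional. As written, inclusion can depend on arm, and no section says whether patients who fail the check remain in the analysis. A reader might go further and conclude that successes are in fact screened out and lost. The documents do not show that. It would require drug changes before the patient's own entry, recorded in time for the check, and removal of those patients from the analysis.

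If they are removed, the bias is toward no effect, so it would not by itself create a false claim of benefit. At L = 0.40 it is modest at 10% to 25% carry-over: about 1 to 2.4 points off a planned 30-point difference, with power of 89% to 86%. At 50% it matters more: about 5 points, with power of 79%. With no carry-over and the same check in both arms, the loss is zero. The 20% allowance in section 11.1 covers lost numbers, not selective loss. The figures rest on random entry over 5 weeks, the plan's 35% and 5% rates, and the assumed carry-over share.

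**What to change.** In sections 6.4, 6.5 and 9.1:

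- Fix each clinician's patient list and eligibility on one date, at or before that clinician's randomisation and before the first message, in the same way for both arms.
- Apply any later re-check identically in both arms, and use it only to decide whether the strategy is delivered.
- Keep every listed patient in the ITT analysis, saying so in section 11.2, and report re-check failures by arm with reasons.

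The cost is a change of wording and a few more patients to follow up. The downside is that a few patients who became ineligible before delivery stay in ITT and slightly dilute the contrast.

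Entering a clinician's patients in the same week would also help, but it is optional. The weekly capacity of 28 in section 5.2 does not guarantee that it is feasible: section 9.1 sets capacity per nurse, and section 11.1 aims to avoid many notifications to one clinician in a short time.

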6.5 Screen Failures

Patients who are ineligible for the study at the time of screening will not be included.

6.6 Strategies for Recruitment and Retention

This trial will be conducted as a pragmatic quality improvement initiative in partnership with the Michigan Medicine anticoagulation monitoring service. There will therefore not be a formal recruitment process. No strategies will be used for participant retention.

7 STUDY IMPLEMENTATION STRATEGIES

7.1 Quality Improvement Strategy Descriptions

The clinician notification process has been formalized as a clinical protocol approved by the anticoagulation clinic to address upper GI bleeding risk. As part of routine care, the QI strategy will be delivered by the anticoagulation nurses assigned to each of 7 anticoagulation clinic teams.

Clinician Notification (CNNF): An anticoagulation clinic nurse sends a templated message to the patient's target clinician that identifies the patient as high risk for upper GI bleeding, summarizes guidelines on appropriate antiplatelet drug use and PPI gastroprotection, and recommends that the clinician consider either discontinuing the patient's antiplatelet drug or initiating a PPI for gastroprotection. The nurse will also offer to pend the order for a PPI if the clinician wants to initiate a PPI and will provide education to the patient on any medication changes recommended by the clinician.

Usual care: With usual care, the anticoagulation clinic will not send the clinician notification letter or other project-specific materials to the clinician or patient.

7.2 Fidelity

7.2.1 Anticoagulation Nurse Training

Prior to commencing the quality improvement initiative, the anticoagulation clinic staff will attend an instructional meeting with a research team member on how and when to administer the QI strategy components and how to document delivery of strategies in the EHR. This training is anticipated to be 60 minutes long.

For anticoagulation clinic staff, the implementation strategies and how to perform them are additionally described in anticoagulation clinic protocol documents.

During week 1 of the trial, the research team will audit the charts of all patients randomized to CNNF and meet with the anticoagulation nurses to provide feedback if there were any discrepancies in delivery of the intervention. A similar meeting will recur in later weeks if discrepancies continue.

Fidelity will be assessed during the week 7-10 chart review for all patients to ensure that they received the QI strategy to which they were randomized.

7.2.2 Quality Improvement Strategy Delivery

Anticoagulation clinic nurses will have templated written materials to use as part of CNNF.

Nurses will also have an example script available to use when talking with patients about medication changes if the clinician requests that the nurse provide patient education.

7.2.3 Quality Improvement Strategy Receipt & Enactment

Chart review will be performed for patients whose clinicians were randomized to the clinician notification (CNNF) arm to ensure that the implementation strategy was delivered as intended and that the strategies had fidelity. A fidelity checklist will be used.

7.3 Measures to Minimize Bias: Randomization and Blinding

Assignment of clinicians to CNNF vs. usual care will be done at the cluster level according to the identity of the clinician to be contacted. Clinicians will be stratified by treating small vs. large numbers of patients eligible for the trial, and by procedural vs. non-procedural specialist. The cluster of patients cared for by each anticoagulation clinic target clinician will be randomized 1:1 to get either clinician notification with nurse facilitation (CNNF) or usual care. Randomization will be carried out by the study statistician. For each included clinician, up to 4 patients will be included in their cluster (see section 11.1 for justification). For clinicians with more than 4 eligible patients in their cluster, 4 patients will be selected at random.

Neither patients, clinicians, or anticoagulation staff can practically be blinded. We will attempt to blind the research staff who are making patient calls at week 7-10 to the randomization group of the patient by not providing them with any information that would allow them to infer the randomization group, by not having them enter MiChart for the patients, where such information could be obtained, and by excluding any information from the call script that might help identify the randomization group. However, if due to staffing or personnel issues, blinded research staff are unable to complete all calls within the specified time frame, unblinded research staff will assist with completing patient calls.

7.4 Concomitant Therapy

Patients in this study will continue to receive all other usual care through the anticoagulation clinic. They will not be prevented from seeking or being exposed to any other medications or information from other sources during the study period or from seeking care from other clinicians.

7.5 Rescue Therapy

N/A

8 END-OF-INTERVENTION/END-OF-STUDY

8.1 Discontinuation of Intervention

The QI strategies will not be delivered to patients who discontinue warfarin therapy or are closed to the anticoagulation monitoring service between the time of randomization and the

anticipated date of QI strategy delivery. Patients who discontinue warfarin therapy or are closed to the anticoagulation monitoring service after QI strategy delivery but before week 7-10 will not be assessed by phone at week 7-10, though chart review will still be completed for these patients. The QI strategies will additionally not be delivered to patients whose target clinician on the report changes between the time of randomization and the anticipated date of QI strategy delivery. However, patients whose target clinician changes after QI strategy delivery but before week 7-10 will still be assessed at week 7-10.

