The study is designed as a pragmatic cluster randomized quality improvement trial. For each patient, a target clinician will be identified, defined as either a cardiologist at Michigan Medicine, if the patient has seen one in the past year, or else the patient's primary care provider if within Michigan Medicine, or else the clinician of record on file with the anticoagulation service. For each patient, assignment to receipt of the quality improvement strategy vs. usual care will be done at the cluster level according to the identity of the target clinician. Each clinician (cluster) will be randomized 1:1 to receive either clinician notification with nurse facilitation (CNNF), consisting of a notification message sent in the electronic health record, or to a usual care arm. Each clinician cluster will be limited to 4 or fewer patients. Following delivery of the quality improvement (QI) strategy to clinicians in the CNNF arm, the study team will conduct phone surveys with all patients whose clinicians received usual care or CNNF and perform chart review in the medical record to evaluate the effect of CNNF on reducing upper GI bleeding risk through discontinuation of all antiplatelet drugs or initiation of PPI co-therapy.

Primary Objective: To determine the extent to which clinician notification with nurse facilitation (CNNF) versus usual care is associated with differences in the proportion of patients who have medication optimization (defined as either discontinuation of all antiplatelet drugs or initiation and adherence to a PPI) at week 7-10.

Secondary Objectives: To determine the extent to which CNNF (vs usual care) is associated with differences in the proportion of patients who are recommended to have medication optimization based on chart review after 6 weeks.

Endpoints*:

Primary Endpoint: The proportion of patients who self-report either discontinuing all antiplatelet therapy (defined as none in the past 7 days) or initiation and adherence to a proton pump inhibitor (defined as use for at least 5 of the prior 7 days) at week 7-10.

Secondary Endpoints:

[figure not shown]
- The proportion of patients with a documented recommendation in the electronic health record to either discontinue all antiplatelet therapy or initiate a PPI

Phase or Stage:

Randomized quality improvement project with a wait-list control group

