8.3 Lost to Follow-Up

For patients unable to be reached for the phone survey at week 7-10, chart review will still be performed.

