9.2 Assessment of the Primary Endpoint

The primary endpoint, defined as the proportion of patients for whom medication optimization was achieved (defined as either discontinuation of all antiplatelet therapy or initiation and

adherence to a proton pump inhibitor) will be determined by patient reported medication use at week 7-10. Up to three attempts will be made to contact patients by phone over the course of 4 weeks to assess the primary endpoint. The phone call is anticipated to take not more than 5 minutes. With calls 1 and 3, a brief message will be left stating the research assistant's name and affiliation with the anticoagulation clinic and asking the patient to call back at their earliest convenience. A script has been developed to guide the phone survey. If the patient self-reports any use or non-use of medications that contradicts the information in their MiChart medication list, the research assistant will send a message to the patient's anticoagulation clinic nurse so that the nurse can reconcile the chart. No remuneration will be offered with this patient assessment. We request a waiver of informed consent for this patient phone survey.

There will be no assessments that require physical exams, radiology, biological specimens or laboratory evaluations.

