11.2 General Statistical Approach

For the primary and secondary endpoints, an intention-to-treat analysis approach will be used.

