11.5 Analysis of the Primary Endpoint(s)

We will use generalized linear mixed effects modeling (logit link) to estimate the odds of medication optimization at week 7-10. This model will include fixed effects for CNNF (vs. usual care), target provider specialty and size, and a random effect for clinician to account for the clustering of patients. We will report the odds ratios with corresponding confidence intervals for the main effect. The main effect will be tested at a two-sided 5% significance level. Sensitivity analyses will adjust for patient age, gender, comorbidities, antiplatelet drug at study entry, and clustering at the nurse level.

For patients who were unable to be contacted by phone for the week 7-10 phone call (lost to follow up), or who declined to participate, we will perform exploratory analyses to determine whether they differed (with respect to demographic characteristics, medical history, or target clinician specialty) from patients who were able to be reached. We will use multiple imputation to account for any missing data for the patients lost to follow up considering all demographic, medical history and target clinician specialty variables considering the data missing at random and combine results across imputation via Rubin's rules. Best and worst case sensitivity

analyses will assess the robustness of the findings and provide the range of uncertainty of conclusions made. For patients who call back the research team after week 10, the survey will still be completed, but their outcome will be considered missing and imputed in primary analysis with a sensitivity analysis using the week 10 outcome.

Patients who reported at the week 7-10 phone call that they were either not using antiplatelet therapy at the start of the trial or were using a PPI will be included in the primary ITT analysis. We expect those who were not initially eligible to be balanced across the groups, thus the comparison of CNNF vs usual care will remain valid; however, for more accurate estimates, we will also conduct a per-protocol analysis where we exclude these individuals.

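### Section 8.1 withholds the week 7-10 call, the only source of the primary endpoint, from randomised patients who stop warfarin or leave the service

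*Combined protocol and SAP*

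**What the plan says.** Section 9.2 takes the primary endpoint from the phone survey: it "will be determined by patient reported medication use at week 7-10". The synopsis describes that survey as the only live patient assessment. Chart review serves the secondary and exploratory endpoints.

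Section 8.1 covers patients who stop warfarin or are closed to the service after the quality improvement strategy is delivered and before week 7-10. They "will not be assessed by phone at week 7-10, though chart review will still be completed for these patients". The same section treats a change of target clinician after delivery differently: those patients are still assessed.

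Other parts of the plan point the other way:

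- Synopsis, study description: "the study team will conduct phone surveys with all patients whose clinicians received usual care or CNNF".
- Section 11.2: "For the primary and secondary endpoints, an intention-to-treat analysis approach will be used".

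On when delivery happens, the synopsis ties it to clinicians in the clinician notification with nurse facilitation (CNNF) arm. Section 5.2 says of the other arm: "At the completion of the study, the patients who were randomized to the wait-list control group will receive the quality improvement strategy". Section 7.2.1 uses the term more broadly, with charts of all patients reviewed "to ensure that they received the QI strategy to which they were randomized".

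On missing outcomes, section 8.3 states: "For patients unable to be reached for the phone survey at week 7-10, chart review will still be performed". Section 11.5 first describes patients who could not be contacted or who declined, then states: "We will use multiple imputation to account for any missing data for the patients lost to follow up". It adds best- and worst-case sensitivity analyses.

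**The concern.** Patients affected by the rule have been randomised, and the endpoint is still defined for them, because it asks about antiplatelet and PPI use and does not require ongoing warfarin. The protocol simply chooses not to ask. The chart review they still receive cannot supply a self-reported outcome.

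Three things follow.

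- **Avoidable missing outcomes.** The loss is triggered by events after randomisation, which cannot be assumed independent of arm. If these patients are dropped, the primary analysis is not intention-to-treat.
- **No common clock.** The rule starts at delivery. Read literally, only CNNF patients can meet it. If delivery is meant to cover both arms, no matching date is given for usual care. On either reading, staff could apply the rule differently by arm.
- **Unstated analysis.** A patient deliberately not called was neither unreachable nor unwilling. If such patients are left out of the best- and worst-case analyses, the reported range of uncertainty is too narrow.

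**Working it through.** **Step 1. The plan's own sample size.** Inputs from section 11.1: rates of 5% and 35%, 90% power, two-sided 5% type I error, ICC 0.95, coefficient of variation of cluster size 0.62, mean of 2 patients per clinician, 20% dropout or ineligibility.

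- Unclustered size per arm, unpooled variance: (1.960 + 1.282)² × (0.05×0.95 + 0.35×0.65) / 0.30² = 32.1.
- Design effect: 1 + [(1 + 0.62²)×2 − 1]×0.95 = 2.680.
- 32.1 × 2.680 = 86.06 patients per arm, hence 44 clinicians per arm and 176 patients.
- 176 / 0.8 = 220, or 110 per arm. The allowance is 220 − 176 = 44 patients.

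The stated 176 and 220 reproduce. The sample size is not at issue.

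**Step 2. How many are affected.** The documents give no rate of stopping warfarin or leaving the service. Section 6.2 requires anticipated warfarin use of at least 90 days, and participation lasts 10 weeks (70 days), so the number is probably small. The shares r of 2%, 5% and 10% below are assumptions.

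**Step 3. Illustration (a): uncalled patients in CNNF only, dropped without imputation.** The true rates are the planned 35% and 5%.

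- Every uncalled patient was optimised: (0.35 − r)/(1 − r) − 0.05.
- No uncalled patient was optimised: 0.35/(1 − r) − 0.05.

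| r | CNNF patients uncalled (of 110) | Difference if all optimised | Difference if none optimised |
|---|---|---|---|
| 2% | about 2 | 28.7 points | 30.7 points |
| 5% | 5-6 | 26.6 points | 31.8 points |
| 10% | 11 | 22.8 points | 33.9 points |

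The planned difference is 30 points.

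**Step 4. Illustration (b): share r uncalled in each arm, all entered in the best- and worst-case analyses.** Rates among those called are 35% and 5%.

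- Worst case (uncalled CNNF patients fail, uncalled usual-care patients succeed): (1 − r)×0.35 − [(1 − r)×0.05 + r].
- Best case (the reverse): (1 − r)×0.35 + r − (1 − r)×0.05.

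| r | Worst case | Best case | Width |
|---|---|---|---|
| 2% | 27.4 | 31.4 | 4 points |
| 5% | 23.5 | 33.5 | 10 points |
| 10% | 17.0 | 37.0 | 20 points |

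The width is 2r, so each 1% uncalled per arm adds 2 points. That width is hidden if these patients are left out.

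**Step 5. Power.** Suppose the loss comes on top of the full 20% allowance. Power is Φ(0.30/√[0.275×2.680/n] − 1.960), where 0.275 = 0.05×0.95 + 0.35×0.65.

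| Extra loss | n per arm | Power |
|---|---|---|
| 0% | 88 | 90.6% |
| 2% | 85.8 | 89.9% |
| 5% | 82.5 | 88.8% |
| 10% | 77 | 86.6% |

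If these patients fall within the 20%, nothing is lost against the plan.

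**The case against.** The strongest reply has four parts.

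*There is a common clock.* Both arms enter in weekly batches and follow one schedule, and section 8.1 itself mentions an anticipated delivery date, so delivery can be read as the entry week. That is plausible, and the documents do not show that loss differs by arm. But the no-call rule does not use that date. The point supports writing the entry week into the rule.

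*Nothing excludes these patients from the analysis.* The best- and worst-case sentence has no population limit, late callers are expressly imputed, and the imputation wording looks loose. This is fair: no passage says that the group will be dropped. Equally, none says that it will be included, and a prespecified plan should not rest on a generous reading. Imputation is also a weaker answer than asking. If patients who stop warfarin before the call are never called, their values must be borrowed from patients who continued.

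*Warfarin cessation changes what the endpoint means.* The trial concerns combined therapy, and a patient off warfarin no longer takes it. Counting such a patient as observed is a choice about the question being asked, and it should be stated. It does not justify leaving the outcome uncollected. The endpoint definition does not require warfarin, and section 11.5 already keeps in the primary analysis patients who report that they did not meet the medication criteria at the start.

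*The effect is small.* With the design effect of 2.68 and no other losses, a 22.8-point difference (99 against 110 patients) still gives z of about 2.8. The 5% worst case of 23.5 points gives about 2.7. Only the 10% worst case falls below 1.96, and nothing in the documents supports that share. This stands, and it limits the severity.

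That the synopsis is only a summary also has some force, but reading section 8.1 as an exception to it does not restore the outcomes that intention-to-treat needs.

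**Conclusion.** The concern holds and should be fixed. Followed exactly, section 8.1 leaves the primary outcome uncollected for some randomised patients because of what happens after randomisation. It conflicts with the synopsis and with section 11.2, it has no defined start in usual care, and section 11.5 does not place these patients in any missing-data category.

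The consequence is possible bias of unknown and probably small size. On the assumed shares of 2% to 10%, it moves a 30-point difference by at most about 7 points (30 − 22.8 = 7.2), and that requires one-sided loss, no imputation and identical outcomes in every uncalled patient. There is no evidence of differential loss, and power is little affected. The conflict between the passages is certain; the numerical effect rests entirely on assumed shares.

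**What to change.** 1. In section 8.1, define one index date for both arms, for example scheduled study entry.
2. Attempt the week 7-10 call for every randomised patient in both arms, whatever their later warfarin status, clinic enrolment, change of target clinician or receipt of CNNF, and analyse the answers as observed. Reconcile section 8.1 with the synopsis accordingly.
3. State that the weekly eligibility re-check in section 9.1 decides delivery only, not outcome collection or analysis. Section 8.1 does not say whether patients who leave before delivery are called; this would settle it.
4. In section 11.5, state that any randomised patient without a week 7-10 call, for whatever reason, enters the multiple imputation and the best- and worst-case analyses.
5. Report exits by arm and reason.

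These changes concern outcome collection and analysis only, not clinical care. The cost is protocol and SAP wording and a few extra calls of about five minutes by existing staff. Some calls will go to patients no longer on warfarin or no longer followed by the clinic. The waiver in section 12.1.1.2 is justified partly by the clinic's need for accurate records on warfarin-related risk, so it should be checked that it covers them.
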